**E16g. During the last seven days, how frequently have you felt an urgent need to use heroin/opioids? [odas5a]**

1 - More than twice every day	2 - Every day at least once or twice a day	3 - Three to six times in the last seven days	4 - One or two times in the last seven days	5 - None
-------------------------------	--	---	---	----------

If [5] → skip to E16i

**E16h. During the last seven days, how intensely did you feel the need to use heroin/opioids, on average on a scale of 1-5? A 1 would mean extremely intense and a 5 would mean nothing at all.? [odas5b]**

1 - 'Extremely intense'	2 -	3 -	4 -	5 - 'Nothing at all'
-------------------------	-----	-----	-----	----------------------

**E16i. During the last seven days, how frequently have you had any symptoms of overmedication of methadone? (such as feeling sleepy or sedated, difficulty in speaking, being unusually active or, alternatively, the sensation of "being drugged") [odas6a]**

None... 5 points [5]

1-2 times... 4 points [4]

3-6 times... 3 points [3]

Every day, once or twice a day... 2 points [2]

Page 60 of 144

Brown University IRB Original Approval: 04/18/2019

Brown University IRB Amendment Approval: 11/22/2020

Brown University IRB Amendment Approval: 08/10/2020

Brown University IRB Amendment Approval: 10/15/2020

Brown University IRB Amendment Approval: 02/26/2021

Brown University IRB Original Approval/Continuing Review Approval: 03/18/2021

Brown University IRB Amendment Approval: 06/15/2021

Brown University IRB Amendment Approval: 09/01/2021

Brown University IRB Amendment Approval: 10/05/2021

Brown University IRB Amendment Approval: 10/15/2020

Brown University IRB Amendment Approval: 02/26/2021

Brown University IRB Continuing Review Approval: 03/18/2021

Brown University IRB Amendment Approval: 06/15/2021

Brown University IRB Amendment Approval: 09/01/2021

Brown University IRB Amendment Approval: 10/05/2021

BROWN

School of Public Health

Brown University IRB Amendment Approval: 11/09/2021

Brown University IRB Amendment Approval: 12/13/2021

More than twice every day... 1 points [1]

**E16j. During the last seven days, how intense were the overmedication symptoms you felt on a scale of 1-5? A 1 would mean extremely intense and a 5 would mean nothing at all. [odas6b]**

1 - 'Extremely intense'	2 -	3 -	4 -	5 - 'Nothing at all'
-------------------------------	-----	-----	-----	-------------------------

**E17. What is your current health insurance coverage? [inssts]**

No insurance [1]

Insurance through my workplace [2]

Medicare/Medicaid or other governmental insurance like Neighborhood Health Plan [3]

Individual/family private coverage [4]

Other [77]

DK/R [99]

**E17a. If inssts= "other": What is your current health insurance coverage:\_\_\_\_\_ [inssts\_oth]**

**E18. Have you ever been diagnosed with a mental health or cognitive disorder? [mentdiagevr]**

Yes

No

DK/R

**E19. If mentdiagevr= "yes" What mental health disorder were you diagnosed with? (Read out list; check all that apply) [mentdiagname]**

Attention-Deficit/Hyperactivity Disorder (ADD/ADHD) [1]

Obsessive-compulsive disorder (OCD) [2]

Eating disorders (like anorexia or bulimia) [3]

Depressive disorder (like major depression) [4]

Bipolar disorder (like manic depressive disorder) [5]

Anxiety disorder (like panic attacks or phobias) [6]

Psychosis (like schizophrenia, brief psychotic episode, or paranoia) [7]

Another diagnoses [77]

No, none of the above [0]

DK/R [99]

**E19a. If mendiagname= "Another diagnoses": What mental health disorder were you diagnosed with:\_\_\_\_\_ [mentdiagname\_oth]**

**E20. Have you ever been hospitalized because of this mental health disorder or injuries caused by the disorder? [hospdis]**

Yes

No

DK/R

**E21. Have you ever been prescribed opioids as a result of injury or acute pain? [presinj]**

Yes

No

DK/R

*Interviewer prompt: We are going to ask you two questions about chronic pain. When we say chronic pain, we mean pain on most days or every day.*

**E21a. In the past six months, how often did you have pain? [pn6m]**

Never	Some days	Most days	Everyday	DK/R
-------	-----------	-----------	----------	------

**E21b. Over the past six months, how often did pain limit your life or work activities? [adl6m]**

Never	Some days	Most days	Everyday	DK/R
-------	-----------	-----------	----------	------

**E22. Have you been prescribed opioids in the past month? [presmnth]**

Yes

No

DK/R

**E23. Have you ever been denied opioid medications for painful conditions? [op\_den]**

Yes

No

DK/R

**E24. If op\_den= "yes": What was the reason for denial? (Read out list; check all that apply) [op\_den\_reason]**

No reason given [1]

Being homeless [2]

Not having health insurance [3]

Page 62 of 144

Brown University IRB Original Approval: 04/18/2019

Brown University IRB Amendment Approval: 11/22/2020

Brown University IRB Amendment Approval: 08/10/2020

Brown University IRB Amendment Approval: 10/15/2020

Brown University IRB Amendment Approval: 02/26/2021

Brown University IRB Continuing Review Approval: 03/18/2021

Brown University IRB Amendment Approval: 06/15/2021

Brown University IRB Amendment Approval: 09/01/2021

Brown University IRB Amendment Approval: 10/05/2021

Brown University IRB Amendment Approval: 10/15/2020

Brown University IRB Amendment Approval: 02/26/2021

Brown University IRB Continuing Review Approval: 03/18/2021

Brown University IRB Amendment Approval: 06/15/2021

Brown University IRB Amendment Approval: 09/01/2021

Brown University IRB Amendment Approval: 10/05/2021

BROWN

School of Public Health

Brown University IRB Amendment Approval: 11/09/2021

Brown University IRB Amendment Approval: 12/13/2021

Revised & Approved 11/22/2019

Revised & Approved 12/09/2019

Administrative correction submitted 12/12/2019

Revised & Approved 08/17/2020

Revised and Approved: 10/15/2020

Revised and Approved 02/01/2021

Revised and Approved: 09/01/2021

Physician denied because of diversion or substance use concerns [4]

Clinic does not prescribe narcotics [5]

Did not see my regular physician [6]

Physician said pain wasn't serious enough or other medications are sufficient [7]

Physician concerned about adverse effects [8]

Positive drug test [9]

Other [77]

DK/R [99]

**E24a. If op\_den\_reason= "other": What was the reason for denial: \_\_\_\_\_ [op\_den\_reason\_oth]**

3

≥4

DK/R

*Interviewer prompt: Please indicate how much you agree or disagree with the following statements:*

**F7. I am confident that I can recognize when someone is having an opioid overdose. [motiv11]**

Strongly disagree	Disagree	Neutral	Agree	Strongly agree	DK/R
-------------------	----------	---------	-------	----------------	------

**F8. I am confident that I would call 911 if a friend or family member were overdosing. [motiv12]**

Strongly disagree	Disagree	Neutral	Agree	Strongly agree	DK/R
-------------------	----------	---------	-------	----------------	------

**F9. I am confident that I would call 911 if a friend or family member were overdosing, even if drugs or drug paraphernalia were present at the scene. [motiv13]**

Strongly disagree	Disagree	Neutral	Agree	Strongly agree	DK/R
-------------------	----------	---------	-------	----------------	------

**F10. I am confident that I would call 911 if a friend or family member were overdosing, even if I was high on drugs. [motiv14]**

Strongly disagree	Disagree	Neutral	Agree	Strongly agree	DK/R
-------------------	----------	---------	-------	----------------	------

**F11. I am worried that other people might think that I am using drugs if they see me carrying naloxone (a medicine that can reverse an overdose). [motiv15]**

Strongly disagree	Disagree	Neutral	Agree	Strongly agree	DK/R
-------------------	----------	---------	-------	----------------	------

**F12. What do you do to avoid an accidental overdose? (Read out list; check all that apply) [skill6]**

Page 65 of 144

Brown University IRB Original Approval: 04/18/2019

Brown University IRB Amendment Approval: 11/22/2020

Brown University IRB Amendment Approval: 08/10/2020

Brown University IRB Amendment Approval: 10/15/2020

Brown University IRB Amendment Approval: 02/26/2021

Brown University IRB Continuing Review Approval: 03/18/2021

Brown University IRB Amendment Approval: 06/15/2021

Brown University IRB Amendment Approval: 09/01/2021

Brown University IRB Amendment Approval: 10/05/2021

Brown University IRB Amendment Approval: 10/15/2020

Brown University IRB Amendment Approval: 02/26/2021

Brown University IRB Continuing Review Approval: 03/18/2021

Brown University IRB Amendment Approval: 06/15/2021

Brown University IRB Amendment Approval: 09/01/2021

Brown University IRB Amendment Approval: 10/05/2021

BROWN

School of Public Health

Brown University IRB Amendment Approval: 11/09/2021

Brown University IRB Amendment Approval: 12/13/2021

Nothing [1]

Avoid mixing with alcohol [2]

Avoid mixing with other drugs [3]

Smell or taste my supply [4]

Using with someone else [5]

Take smaller amounts [6]

Go slow [7]

Take a tester [8]

Use a fentanyl test strip [9]

Keep Narcan/naloxone nearby [10]

Change supplier or dealer [11]

Something else [77]

DK/R [99]

**F12a. If skill6= "other": What do you do to avoid an accidental overdose: \_\_\_\_\_ [skill6\_oth]**

**F12b. Has COVID-19 changed any of the ways that you protect yourself from an overdose?**

(Read out list; check all that apply) [cov\_skill6]

COVID-19 has not changed how I protect myself from an overdose [1]

I have not been able to get naloxone [2]

I have not been able to get fentanyl test strips [3]

I have started using with different people[4]

I have had to use alone [5]

I have not been able to buy from my usual dealer [6]

Something else [77]

DK/R [99]

**F12c. If cov\_skill6="Something else": How has COVID-19 impacted the ways that you protect yourself from an overdose? \_\_\_\_\_ [cov\_skill6\_oth]**

*Interviewer prompt: We'd now like to ask you about your own experience with accidental overdose. By accidental overdose we mean taking too much of a drug such that someone is no longer able to respond or breathe adequately. Other symptoms of an accidental overdose can include loss of consciousness, lips turning black or grey, gurgling noises, blacking out, or others. An overdose can occur with prescription or illicit drugs, or a combination of both.*

**F13. Have you ever overdosed by accident? [skill7]**

Yes

No

DK/R

*Interviewer prompt: We'd like to ask you a little more about your experiences of overdosing by accident.*

**F14. If skill7= "yes": Has anyone ever given a dose of naloxone/Narcan to you because they thought you had overdosed by accident? [narcevr]**

Yes

No

DK/R

**F14a. If skill7= "yes": Have you accidentally overdosed in the last month? [skill8]**

Yes

No

DK/R

**F15. If skill8= "yes": In the last month, have you experienced any of the following unwanted negative reactions from using too much of any of the drugs that you have used? (Read out list; check all that apply) [odsympij]**

Lost consciousness/blacked out [1]

Blue or gray lips or skin [2]

Seizure [3]

Had a hard time breathing [4]

Elevated breathing [5]

Stopped breathing [6]

Inability to talk [7]

Not responsive to stimulus (like having your name called or physical contact) [8]

Overheating [9]

Irregular heart beat (fast, slow, irregular or palpitations) [10]

Paranoia [11]

Can't remember getting high [12]

None [0]

Other [77]

DK/R [99]

**F15a. If odsympij= "other": In the last month, have you experienced any of the following unwanted negative reactions from using too much of any of the drugs that you have used: \_\_\_\_\_ [odsympij\_oth]**

**F16. If skill8= "yes": How many times have you overdosed in the last month? [odnumb]**

\_\_\_\_\_ (integer, allowable range 1 to 30)

DK/R

**F17. If skill8= “yes”: Now we want to ask you about the most recent time you overdosed. Who was with you the last time you overdosed? (Read out list; check all that apply) [odw]**

- A close friend [1]
- A casual friend or acquaintance [2]
- A sex partner [3]
- An immediate family or household member [4]
- An extended family member [5]
- A dealer [6]
- A stranger (like people on the street) [7]
- I was alone [8]
- DK/R [99]

**F17a. If skill8= “yes”: The last time you overdosed, what drug(s) did you intend to take? (Read out list; check all that apply) [drgintend]**

- Prescription opioids such as Percocet, OxyContin, Dillaudid, Vicodin [1]
- Medications used for opioid use disorder such as Methadone, buprenorphine/Suboxone [2]
- Benzodiazepines/Benzos such as Xanax, Ativan, Valium, Klonapin [3]
- Prescription stimulants such as Adderall, Ritalin, Focalin, Concerta, Dexedrine [4]
- Marijuana or hash oil, including edibles and synthetic marijuana [5]
- Club drugs such as Molly, MDMA, Ecstasy, GHB, Ketamine [6]
- Psychedelics, such as Mushrooms, Acid, LSD, DMT [7]
- Crystal methamphetamine (crystal meth, glass, ice, tina) [8]
- Powder cocaine [9]
- Crack cocaine [10]
- Heroin [11]
- Other [77]
- DK/R [99]

**F17aa. If drgintend= “other”: The last time you overdosed, what drug(s) did you intent to take: \_\_\_\_\_ [drgintend\_oth]**

**F17b. If skill8= “yes”: The last time you overdosed, did you overdose on a drug that you thought might have contained fentanyl? [odfentsuspect]**

- Yes
- No
- DK/R

**F17c. If odfentsuspect= “yes”: The last time you overdosed on a drug that might have contained fentanyl, did you know it had fentanyl in it before you used it? [fentknwbfr]**

- Yes
- No

Page 68 of 144

Brown University IRB Original Approval: 04/18/2019

Brown University IRB Amendment Approval: 11/22/2020

Brown University IRB Amendment Approval: 08/10/2020

Brown University IRB Amendment Approval: 10/15/2020

Brown University IRB Amendment Approval: 02/26/2021

Brown University IRB Original Approval/Continuing Review Approval: 03/18/2021

Brown University IRB Amendment Approval: 06/15/2021

Brown University IRB Amendment Approval: 09/01/2021

Brown University IRB Amendment Approval: 10/05/2021

Brown University IRB Amendment Approval: 10/15/2020

Brown University IRB Amendment Approval: 02/26/2021

**BROWN**  
School of Public Health

Brown University IRB Amendment Approval: 11/09/2021

Brown University IRB Amendment Approval: 12/13/2021

DK/R [DK]

**F17d. If *odfentsuspect*= "yes": The last time you overdosed, what reaction did you have to the drug or drugs mentioned above? (Read out list; check all that apply) [drgrct]**

Lost consciousness/blacked out [1]

Blue or gray lips or skin [2]

Seizure [3]

Had a hard time breathing [4]

Elevated breathing [5]

Stopped breathing [6]

Inability to talk [7]

Not responsive to stimulus (like having your name called or physical contact) [8]

Overheating [9]

Irregular heart beat (fast, slow, irregular or palpitations) [10]

Paranoia [11]

Can't remember getting high [12]

None [0]

Other [77]

DK/R [99]

**F17da. If *drgrct*= "other": The last time you overdosed, what reaction did you have to the drug or drugs mentioned above: \_\_\_\_\_ [drgrct\_oth]****F17e. Where were you the last time you overdosed? [odplc]**

Own place (room or apartment)

Partner's place

Friend's place

Dealer's place

Street (alley, doorway, etc.)

Bathroom (any public washroom)

Park

Youth drop-in center

Parking lot

Car

Inside club or bar

House party

School

Abandoned house or building

Jail or prison

Crack house/shooting gallery

Other: \_\_\_\_\_

DK/R

**F18. If skill8= "yes": The last time you overdosed, did someone with you call 911? [odcall]**

Yes

No

DK/R

**F19. If skill8= "yes": The last time you overdosed, did someone administer naloxone/Narcan? [odnarc]**

Yes

No

DK/R

**F20. If odnarc= "yes": The last time you overdosed, who gave you naloxone/Narcan? (Read out list; check all that apply). [narcw]**

A police officer [1]

An ambulance official [2]

A health professional [3]

A friend [4]

A parent or relative [5]

Another person using drugs [6]

A stranger [7]

Someone else [77]

DK/R [99]

**F20a. If narcw= "other": The last time you overdosed, who gave you naloxone/Narcan: \_\_\_\_\_ [narcw\_oth]**

**F21. If skill8= "yes": The last time you overdosed, were you taken to the hospital? [odhosp]**

Yes

No

DK/R

**F22. If odhosp= "yes": The last time you overdosed and were taken to a hospital, were you offered referral to an addiction treatment program before discharge? [hoptxt]**

Yes

No

DK/R

**F23. If odhosp= "yes": The last time you overdosed and were taken to a hospital, were you given naloxone/Narcan at discharge? [hospnx]**

Yes

No

DK/R

**F24. If odhosp= "yes": The last time you overdosed and were taken to a hospital, did you see a peer recovery specialist, also known as a peer recovery coach? [peernx]**

Yes

No

DK/R

**F24a. If skill8= "yes": In the month before your last overdose, were you in any of the following programs? (Read out list; check all that apply) [trtdurod]**

Detoxification [1]

Methadone [2]

Buprenorphine/Suboxone/Subutex treatment [3]

Self-help group (like 12-step AA, NA) [4]

Outpatient drug or alcohol treatment program [5]

Day treatment program or partial hospitalization program [6]

Residential drug treatment program [7]

Another kind of treatment [8]

Jail or prison [9]

None of the above [10]

DK/R [99]

**F27. I am concerned about my friends overdosing [motiv16]**

Strongly disagree	Disagree	Neutral	Agree	Strongly agree	DK/R
-------------------	----------	---------	-------	----------------	------

**F28. I am concerned about overdosing [motiv17]**

Programmer Note: PIPE response to free text before intervention, G0.

Strongly disagree	Disagree	Neutral	Agree	Strongly agree	DK/R
-------------------	----------	---------	-------	----------------	------

**F29. I get the support and resources I need from others to help me avoid an overdose. [skill9]**

Programmer Note: PIPE response to free text before intervention, G0.

Strongly disagree	Disagree	Neutral	Agree	Strongly agree	DK/R
-------------------	----------	---------	-------	----------------	------

**F30. I am confident that I can ask someone to check on me after I use drugs, and call 911 if they think I am overdosing. [motiv18]**

Strongly disagree	Disagree	Neutral	Agree	Strongly agree	DK/R
-------------------	----------	---------	-------	----------------	------

## **Egocentric Network Assessment Tool (ENAT)**

**Nomination question:**

*Interviewer prompt: Next, I have a few questions about people in your social network. People who are part of your social network are people you know. This may include friends, family members, coworkers, sexual partners, or people you use drugs with.*

**ENAT1. In the past 90 days, did someone you know experience an overdose? [enat\_nom]**

Yes

No → skip to Overdose Education

DK/R → skip to Overdose Education

**ENAT1a. If enat\_nom="Yes"; In the past 90 days, how many people did you know who experienced an overdose? [enat\_num]**

---

**ENAT 2. Could you tell me the first name of any person you know who overdosed in the past 90 days?**

*Interviewer prompt: Anything you tell me is entirely confidential, but you are welcome to give me nicknames or initials if you would feel more comfortable.*

*(Interviewer: If the respondent lists more than three people, please ask them to name the three most recent). [enat\_name]*

\_\_\_\_\_ [person1]

\_\_\_\_\_ [person2]

\_\_\_\_\_ [person3]

*Interviewer prompt: Next, I have a few questions about your relationship with [pipe person1].*

**ENAT 3. How long have you known [pipe person1]? [enat\_durat]**

\_\_\_\_\_ years        \_\_\_\_\_ months

DK/R [DK]

**ENAT 4. What age is [pipe person1]? (Respondent may provide estimate) [enat\_age]**

\_\_\_\_\_

**ENAT 5. What is [pipe person1]'s gender? (Check only one) [enat\_gend]**

Male [1]

Female [2]

Transgender Male/Trans Man/Female-to-male (FTM) [3]

Transgender Female/Trans Woman/Male-to-Female (MTF) [4]

Genderqueer, neither exclusively male nor female [5]

Something else [77]

DK/R [99]

**ENAT5a. If enat\_gender="Something else": What is [pipe person1]'s gender?: \_\_\_\_\_**  
[enat\_gend\_oth]

**ENAT 6. What is your relationship to [pipe person1]? (Read out list, check all that apply): [enat\_rel]**

A close friend [1]

A casual friend or acquaintance [2]

A sex partner [3]

An immediate family or household member [4]

An extended family member [5]

A Dealer [6]

Strangers/people I don't know [7]

DK/R [99]

**ENAT 7. How close do you feel emotionally to [pipe person1]? (Read out list; check only one) [enat\_close]**

Not close at all [1]

Somewhat close [2]

Very close [3]

Extremely close [4]

DK/R [99]

**ENAT 8. How much do you depend on [pipe person1] for things like money or a place to live or stay? (Read out list; check only one) [enat\_depend]**

Not dependent at all [1]

Somewhat dependent [2]

Very dependent [3]

Extremely dependent [4]

DK/R [99]

**ENAT 9. In the month before the overdose occurred, how often did you spend time with [pipe person1]? (Read out list; check only one) [enat\_time]**

Never [0]

Once or a couple times [1]

At least every week [2]

A couple of times per week [3]

Every day [4]

Multiple times per day [4]

DK/R [99]

**ENAT 10. In the month before the overdose occurred, how often did you and [pipe person1] share drugs or use drugs from the same supplier? [enat\_share]**

Never [0]

Once or a couple times [1]

At least every week [2]

A couple of times per week [3]

Every day [4]

Multiple times per day [4]

DK/R [99]

**ENAT 11. Did you witness the most recent overdose that [pipe person1] experienced? [enat\_witness]**

No [0]

Yes [1]

DK/R [99]

**ENAT 12. The most recent time [pipe person1] overdosed, can you tell me whether the overdose was fatal or nonfatal? [ENAT\_fatal]**

Nonfatal [1]

Fatal [2]

DK/R [99]

*Interviewer prompt: I am going to read a series of statements about how [pipe person1]'s overdosed might have impacted your own drug use.*

Revised & Approved 11/22/2019

Revised & Approved 12/09/2019

Administrative correction submitted 12/12/2019

Revised & Approved 08/17/2020

Revised and Approved: 10/15/2020

Revised and Approved 02/01/2021

Revised and Approved: 09/01/2021

**ENAT 13. Since [pipe person1]’s overdose, which of the following are true for you? (Read out list; check all that apply) [enat\_effect]**

- I use more (frequency or amount) than I did before [1]
- I use less (frequency or amount) than I did before [2]
- I use alone more often [3]
- I use alone less often [4]
- I use when naloxone is available more often [4]
- I use when naloxone is available less often [5]
- I taste or check drugs first more often [6]
- I taste or check drugs first less often [7]
- I use more types of drugs [8]
- I use fewer types of drugs [9]
- I mix drugs more often [10]
- I mix drugs less often [11]
- No difference [12]
- Something else [77]
- DK/R [99]

**ENAT 13a. If enat\_effect= “77”; Is there something else that I didn’t ask you about?: \_\_\_\_\_ [enat\_effect\_oth]**

BROWN

School of Public Health

## **BREAK FOR EDUCATION/INTERVENTION**

*Pipe in response from (ASSIGNED ARM) and answers from questions F12, F27 and F28.*

*If Arm = Control then skip to H1*

*If Arm = Intervention then proceed to G0.*

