**Behavioral Outcomes:** Participants in the intervention arm will be asked a series of questions regarding fentanyl test strip utilization at all follow-up assessments. These questions were used successfully in our pilot study, and include items such as, “Of the 10 tests we gave you, how many tests did you use?” and, “What did you do when you found out your drugs were laced with fentanyl?” As an additional measure of test strip utilization, participants will be asked to return unused tests to the study office. We will also assess motivations for using the test strips, including a desire to avoid IMF-contaminated drugs or purposely identifying fentanyl.

At each time point, participants will be asked about the practices they engage in to avoid accidental overdose. Strategies to avoid overdose include the target overdose risk reduction behaviors:

1. discarding IMF-contaminated drugs,
2. not using alone (and staggering drug use with another person who is able to administer naloxone and call 911 in the event of an overdose), and
3. keeping naloxone nearby.

We will also assess other harm reduction practices, including taking a “tester” or lower initial dose, avoiding injection drug use, and purchasing drugs from a consistent source.

**Standard of Care (Attention-Matched Control Arm).** Existing research suggests that training people who are at risk for overdose and their peers on how to respond when witnessing an overdose is a feasible and effective strategy for preventing overdose death. Given that this represents current overdose prevention practice, participants in the control arm will receive the standardized OEND training that occurs in Rhode Island. This program is based on the common components of many community-based overdose prevention interventions in the US, and includes information on risk factors for overdose, recognizing an overdose, performing rescue breaths, administering naloxone, and recommendations to call 911. **To ensure equivalent attention to the RAPIDS arm, control arm participants will return for retention visits at 1, 2, and 3 months,** and will answer a series of questions regarding substance use and overdose risk behaviors.

**Potential Moderators/Other Key Measures:** The RAPIDS survey instrument will contain additional behavioral, psychological, and clinical assessments asked of everyone in the study. Many of these questions have been piloted successfully in our prior research.

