## **SECTION H: STANDARD OEND** **(CONTROL ARM ONLY)**

**H.0. Now I'm going to show you a video about how to respond to an overdose and how to use naloxone. (<https://vimeo.com/365544296/6685863a30>) I'll also show you how to use naloxone and answer any questions you might have.**

*Programmer prompt: If D30=YES for a participant in the control arm, these additional questions will be asked at the end of the survey.*

*Interviewer prompt: We wanted to ask you a few questions about your experiences using fentanyl test strips because you told us that you used test strips earlier in the survey. For the first XX questions, please tell us how much you disagree or agree with the following statements on a scale of strongly disagree to strongly agree*

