**H1. I feel confident in my ability to test my own drugs for fentanyl. [motiv6\_ctl]**

Strongly disagree	Disagree	Neutral	Agree	Strongly agree	DK/R
-------------------	----------	---------	-------	----------------	------

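### The baseline skip for controls names H1 instead of H.0 and, followed literally, passes over the only control training item in the instrument

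*Protocol*

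**What the plan says.** Protocol section 3.1b describes the comparator: "participants in the control arm will receive the standardized OEND training that occurs in Rhode Island". Section 3.1a and section A1 of the Data and Safety Monitoring Plan say the same.

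In Attachment A the training sits at the break for education and intervention in the baseline survey. Two adjacent lines route the arms: "If Arm = Control then skip to H1" and "If Arm = Intervention then proceed to G0".

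The control-only Section H opens with the training item, "H.0. Now I'm going to show you a video about how to respond to an overdose and how to use naloxone", followed by a naloxone demonstration and time for questions. A programmer prompt then limits what comes next: "If D30=YES for a participant in the control arm, these additional questions will be asked at the end of the survey". D30 asks whether the participant has ever used a fentanyl test strip. H1, the first of those questions, asks for agreement with "I feel confident in my ability to test my own drugs for fentanyl".

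**The concern.** The two routing lines are not parallel. The intervention arm lands on its training item. The control arm lands one item after its training item. A programmer who builds what is printed will never display H.0.

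The trial sets out to compare RAPIDS with standard OEND training. The experimental arm's G.0 shows the same overdose-response and naloxone video, from the same link, as H.0. If H.0 is not shown, the arms differ in OEND as well as in the RAPIDS components. An effect could then not be attributed to adding test strips and motivational interviewing to ordinary overdose education. Controls would also leave with a naloxone kit but without the training the protocol promises them.

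**Working it through.** The plan gives no figure to reproduce, and the point rests on no rate, power or margin. The check is a trace of the printed skip logic.

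1. **Into the break.** The last block before it is the social-network tool. Its first question sends participants who know of no recent overdose onward with "No → skip to Overdose Education", with no condition on arm. Education is therefore expected next for everyone.

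2. **Intervention path.** Break, then G.0: overdose-response and naloxone video, naloxone demonstration, test-strip video, practice, and a discussion noted in text box G.0.a. Training is displayed.

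3. **Control path, read literally.** Break, then H1. H.0 precedes H1 and is not displayed.

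4. **Conflict inside Section H.** The routing line sends all controls to H1. The programmer prompt reserves the questions after H.0 for controls with D30 = yes. For a control who has never used a strip, both instructions cannot hold. Followed together, they leave that person with neither training nor questions.

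5. **Is there a second chance?** Follow-up Section H opens only if C27 (strip use in the last month) is yes, and it contains test-strip questions but no training item. Baseline H.0 is thus the only control training item in the instrument.

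6. **Would the data show an omission?** H.0 has no variable name, response field or completion tick. G.0 at least has its text box, although that box is for behaviour-change goals and does not record that the naloxone video was shown. SAP section 3 plans a modified intention-to-treat analysis that excludes randomised participants who did not receive the intervention. The survey holds no field showing that a control received the control training.

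7. **Number exposed if the literal skip was built.** Planned enrolment is 500, so 500 / 2 = 250 controls. The approved maximum is 550, so 550 / 2 = 275. This is the number at risk under that assumption and not a count of people known to be affected.

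8. **Follow-up routing (minor).** In control Section H, the DK/R answer to H5 goes to G8, and the No and DK/R answers to H10 go to G12. Both targets are in the experimental-arm section. G12 asks about strips obtained beyond the ten supplied by the study, and controls were supplied none.

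**The case against.** A reader might infer from the skip that controls, as the trial is written, do not receive the comparator. The documents do not support that. Three separate descriptions say controls get OEND training. Section H carries standard OEND in its title and is for controls only, so a literal skip would leave H.0 reachable by nobody. The Reopening Plan also lists overdose education as a step of the visit. The coherent reading is that H1 was printed where H.0 was meant.

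Other printed labels in the instrument cannot work literally either. C8, C19 and C23 send all-No answers backwards to C5. Follow-up A5 depends on an answer that A4 does not offer. The control section still contains an unfilled XX. Trained research assistants who see the arm assignment run the visit and may have given the training regardless. All of this stands, and it removes any claim that controls actually went untrained.

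A reader might also infer a bias favouring the intervention on death and on EMS or emergency-department events. Section 3.1b does describe such training as effective against overdose death. However, it trains people to respond to overdoses they witness, whereas the trial counts the participant's own overdoses. It also recommends calling 911, which could raise recorded EMS and emergency-department events, and those are part of the SAP's primary composite. Death enters only an exploratory endpoint. Controls also receive a wallet card, a flyer and printed overdose-prevention material, a partial offset.

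The follow-up skips are small. They reach only controls who reported recent strip use, and they misdirect survey questions without delivering any experimental treatment.

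What survives is narrower. The slip sits in a programming instruction, at the single point where the comparator is delivered. That H1 is evidently an error does not show that it was corrected in the live build.

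**Conclusion.** The point holds as an internal contradiction in how the comparator is delivered. The baseline routing names H1. Protocol sections 3.1a and 3.1b, section A1 of the monitoring plan and Section H itself all require H.0. Followed literally, the skip bypasses the only control training item in the instrument.

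The consequence is conditional. If REDCap was built from the printed skip and staff did not supply the training another way, all 250 to 275 controls received the kit and printed materials without training, and the contrast is not RAPIDS versus standard OEND. Whether this happened cannot be determined from the documents. Neither the size of any resulting bias nor its direction on EMS and emergency-department outcomes can be established. The correction is still worth making, because it concerns the control condition and the survey has no field that would reveal the omission.

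**What to change.** - Change the control branch at the baseline break to proceed to H.0, then show H1 onward only if D30 is yes.
- Add a completion field for the OEND video and naloxone demonstration in both arms, so that receipt of the shared component can be shown.
- Check the live REDCap build, its revision history and any delivery records. If H.0 was ever bypassed, report how many controls missed it and over what dates.
- As a minor correction, re-point follow-up H5 (DK/R) and H10 (No and DK/R) to Section H items. The No answer to H5 already goes to H8, and H14 is the next main question printed after H11.

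The cost is a few routing edits, one field per arm and an administrative amendment. The check of the build takes staff time but no participant contact. Sample size, endpoints and the analysis plan are unchanged unless the check finds controls who were not trained.
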